## 6. STUDY RISKS

**Seed Placement:** The Magseed is placed in an axillary lymph node using local anesthesia in an outpatient environment. There is a small risk of discomfort associated with the local anesthetic. There is a minor risk of infection and bleeding or bruising with the needle entry that is similar to a blood draw. Damage to adjacent structures including vessels or the lung are extremely rare with image guidance.

**MRI:** There is no radiation associated with MRI, but patients with metal devices in their body like pacemakers, cannot have an MRI and will not be able to participate in the study.

Patients with claustrophobia may feel trapped in the MRI scanner and may not tolerate the examination. If the patient feels too confined in the MRI scanner the technologist will stop the examination.

The MRI machine makes loud noises, which can damage hearing. Because of this known risk all patients are required to wear ear protection during the MRI scan that will minimize the discomfort and keep the noise levels at a safe level.

Gadolinium is FDA-approved and routinely used for breast MRI exams. Gadolinium can cause discomfort, warm tingling feeling in the body, metallic taste in the mouth, nausea, or headache in about 1 in 100 patients. These side effects usually last only for a very short time and completely resolve. Severe allergic reactions to gadolinium are extremely rare and occur in about 1 in 300,000 people. The needle placed in the patient's vein may cause minor pain, bruising, or infection at the injection site. Studies have shown that small amounts of gadolinium may remain in the body of patients who have received these injections. The effect of this, if anything, is unknown at this time.

Gadolinium may harm a fetus and therefore, pregnant women will not be allowed to enroll on this study. Women of reproductive age will undergo urine pregnancy testing.

Magseed placement will interfere with visualizing the axilla on MRI. The extent to which the artifact could interfere with visualizing the adjacent breast tissue is unknown. This is way phase 1 will consist of ten patients who have already had all their standard breast imaging. The one-time limited non-contrast MRI will allow us to optimize scanning parameters and decrease the artifact for phase 2 participants receiving their standard MRI after Magseed placement.

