**Mammogram:** Inherent risks include added radiation dose. The MQSA (Mammography Quality Standards Act) recommended average glandular dose limit for screening mammography to 3mGy per view, which equals 12 mGy for a standard 4-view mammogram. There is no set limit for average glandular dose for diagnostic mammography. This is because the number of mammographic views for each patient varies based upon the images necessary to work up any particular finding. All diagnostic mammography will be within current clinical guidelines and well below levels that are known to cause long term side effects.

**Magseed:** The Magseed needle contains bone wax, which contains natural beeswax. There is a potential for a very minimal risk for an allergic reaction or a foreign body reaction (granuloma). To further minimize this risk, patients with known allergies to bone wax, beeswax or propolis will be excluded from the study.

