### Severity of AE:

- Mild – Events require minimal or no treatment and do not interfere with the participant's daily activities.
- Moderate – Events result in a low level of inconvenience or concern with the therapeutic measures. Moderate events may cause some interference with functioning.
- Severe – Events interrupt a participant's usual daily activity and may require systemic drug therapy or other treatment. Severe events are usually potentially life-threatening or incapacitating. Of note, the term "severe" does not necessarily equate to "serious".

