### AE relationship to the study intervention:

- Definitely Related – The AE *is clearly related* to the study intervention.
- Probably Related – The AE *is likely related* to the study intervention.
- Possibly Related – The AE *may be related* to the study intervention.
- Unlikely Related – The AE *is doubtfully related* to the study intervention.

- Not Related – The AE *is clearly NOT related* to the study intervention.

**Expectedness:** Principle investigators and co-investigators will be responsible for determining whether an adverse event (AE) is expected or unexpected. An AE will be considered unexpected if the nature, severity, or frequency of the event is not consistent with the risk information previously described for the study intervention.

- Expected Adverse Events
  - Seed Placement: Minor discomfort, bleeding, infection, bruising
  - MR: Anxiety, stress, claustrophobia
  - Mammography: Anxiety, stress, discomfort
  - Surgical excision of Magseed: Expected discomfort from the operation, bleeding, and infection

**Time Period and Frequency for Event Assessment and Follow-up:** For this study, the study treatment follow-up period is defined as 30 days following the removal of the Magseed. Unanticipated AEs deemed as unrelated or AEs in the mild/grade 1 category do not need to be reported as study data for this study.

**Adverse Event Reporting:** It is the responsibility of the principal investigator to document the grade and attribution of all Adverse Events (AEs) which occur during the course of the study.

The PI will document all AEs that occur within the first 24 hours. AEs will be recoded within the study participant's medical record. The nature of each event, date, time of onset, outcome, frequency, action taken and attribution will be recorded.

**Serious Adverse Event Reporting:** When an adverse event has been identified, the study team will take appropriated action necessary to protect the study participant and then complete the Study Adverse Event Worksheet and log. The principal investigator will evaluate the event and determine the necessary follow-up and reporting required.

**Definition of Unanticipated Problems:** The Office for Human Research Protections (OHRP) considers unanticipated problems involving risks to participants or others to include any incident, experience, or outcome that meets all of the following criteria:

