## 10. DATA MANAGEMENT & STATISTICAL CONSIDERATIONS

**Data Management:** The principle investigator and co-investigators will supervise the data collection management.

**Outcome analysis:** The successful placement of the Magseed into the metastatic axillary lymph node will be evaluated and recorded by the radiologist performing the procedure. This information will be document into the electronic medical records as per normal clinical practice, in addition this information stored in the database.

The degree in which the artifact created by the Magseed in the axilla obscures the axillary or adjacent breast findings will be evaluated and recorded by the radiologist interpreting the MRI. Treatment response based on mammographic and sonographic evaluation of the axilla will be evaluated and recorded by the radiologist. The radiologist will determine if the supplemental imaging with mammography and sonography adequately replaces visualization of the axilla on MRI. Imaging results will be records in standard radiological reports as well as the database.

The successful retrieval of the Magseed into the metastatic axillary lymph node will be evaluated by the surgeon and radiologist. These results will be reported in both the patients operative report as well as the research database.

**Adverse events:** Adverse events occurring during the research study will be recorded into the electronic medical records and recorded into the research database.

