**Data:** Study data will be used to design the data collection instruments and patient data will be entered into a SDMS Database by the study coordinator or other members of the study team. The data collected in will later be exported to the appropriate software for statistical analyses.

**Publications:** Results from this study will be published in a peer reviewed journal.

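### Section 9 lets mild adverse events, including seed-related ones, stay out of the study data, and Section 10 neither repeats nor limits that exception

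*Combined protocol and SAP*

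**What the plan says.** Three places in the combined protocol and SAP decide which AEs reach the analysis.

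- **Section 9**, in the paragraph on the period of event assessment and follow-up: "Unanticipated AEs deemed as unrelated or AEs in the mild/grade 1 category do not need to be reported as study data for this study". The exemption of mild events carries no condition on relatedness.
- **Section 10**, AE paragraph: "Adverse events occurring during the research study will be recorded into the electronic medical records and recorded into the research database". There is no limit by grade or attribution.
- **Section 11 (Ethical Considerations)**, Data paragraph: "patient data will be entered into a SDMS Database by the study coordinator" or another team member, and "The data collected in will later be exported to the appropriate software for statistical analyses".

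The exempt class is described in Section 9 under severity. Mild is defined by "Events require minimal or no treatment and do not interfere with" daily activities. The expected events for placement are given as "Seed Placement: Minor discomfort, bleeding, infection, bruising". Section 6 says of placement: "There is a minor risk of infection and bleeding or bruising with the needle entry that is similar to a blood draw". Under its Magseed heading it also names a possible allergic or foreign body reaction to the wax in the needle.

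**The concern.** Section 1 presents the study as a pilot of both safety and effectiveness. Much of what a percutaneous seed placement is likely to cause is plausibly mild by the protocol's own definition, bruising and minor discomfort being the clearest cases. If those events may be left out of the study data even when the seed or needle caused them, an AE summary drawn from the database can look cleaner than the patients' experience was.

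Consistency is also at stake. Because the exemption is permissive, one team member may enter a mild bruise and another may not, and both follow Section 9. A reader of the final table could not tell whether an empty row for mild events means that none occurred or that none were entered. Section 9 also judges expectedness partly by frequency, and a database that may omit mild related events cannot reliably show that they occur more often than expected.

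**Working it through.** No arithmetic applies. The document gives no AE rates, no grade mix and no planned AE estimate, so the check is a comparison of the texts.

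**Step 1. What happens to each kind of event.** Section 9 is read in the second column as an exception, and Section 10 is read alone in the third.

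| Event | Section 9 as exception | Section 10 alone |
|---|---|---|
| Related, moderate or severe | entered | entered |
| Mild, at least possibly related | may be omitted | entered |
| Mild, unlikely or not related | may be omitted | entered |
| Unanticipated and deemed unrelated, any grade | may be omitted | entered |

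The second row carries this point: an event attributed to the seed or a study procedure may be in the study data or not, depending on the section followed.

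**Step 2. Is there a ranking or cross-reference?** I found none. Section 10 does not mention the exemption, Section 9 does not mention the research database, and neither says which governs.

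**Step 3. Does the difference reach the analysis?** The only export for statistical analysis that is described is from the SDMS database in Section 11. I take this to be the research database of Section 10. That is an inference, but no other study database is described.

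**Step 4. How wide is the mild exemption?** The word *unanticipated* opens the Section 9 sentence. Because the noun is repeated before the mild category, the more natural reading is that it qualifies only the unrelated events, so that all mild events are exempt, including expected bruising or discomfort. If it qualifies both classes, expected mild events are not exempt and only unanticipated mild ones are. The wax reaction is then arguable: Section 6 names it, but the Section 9 list of expected events does not. On either reading some mild events are exempt whatever their relatedness. Grade 1 is not defined separately, so I treat it as the mild category.

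**Step 5. What is still captured elsewhere?** Section 9 has the principal investigator document grade and attribution for all AEs, with recording in the medical record. Unanticipated problems are reported to the IRB with no exemption for mild ones.

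**The case against.** The strongest reply is that the two sections do not conflict. Section 9 is specific and permissive. Section 10 is a general statement of where AEs are stored, and it does not say that every AE must be entered. A specific exception ordinarily limits a general rule, and entering a mild event breaches neither. This stands to the extent that a reader who infers an outright contradiction goes further than the text allows. It does not close the point, because the plan never states the harmonised reading, and that reading is the one under which mild related events may be left out.

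A second reply is that nothing is lost. A reader might infer from the exemption that mild events go unrecorded or that the safety evaluation fails. The document does not support this. The all-AE documentation duty in Section 9 keeps the events in the medical record, and with 20 patients they could be retrieved. Section 9 also mentions a study AE worksheet and log, although under the heading for serious events, so its scope is arguable. IRB reporting covers a mild related event that is unexpected and suggests greater risk. These safeguards reduce the consequence, but none of them puts mild related events into the dataset that is exported.

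A third reply is that Aims 1 to 3 name no safety endpoint. That is correct, and it is a main reason for rating the point low.

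**Conclusion.** The point holds as a minor one, and correcting it is a cheap improvement. As written, the plan permits mild events related to the seed or a procedure to be left out of the study data, and it does not say whether Section 10 is subject to that permission. The effect is confined to the completeness and consistency of the AE summary in a 20-patient pilot. No sample size, error rate or effectiveness result depends on it, and the number of events affected cannot be computed from the document.

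The conclusion assumes that the SDMS database is the research database of Section 10. The examples of expected bruising and discomfort also assume that *unanticipated* does not qualify the mild category. If it does, those examples fall away, but the exemption of unanticipated mild events remains.

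**What to change.** Reconcile Sections 9 and 10 as follows.

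- In Section 9, limit the exemption to mild AEs judged not even possibly related to seed placement, the seed in situ, study imaging or seed removal. On the protocol's five-level attribution scale, these are the mild events rated in the two lowest categories (unlikely related or not related).
- In Section 10, cite that limit, so that AEs of any grade that are at least possibly related to a study procedure are entered in the research database.

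Deleting the exemption altogether is not needed and would cost more. In Part 2 the seed is placed before neoadjuvant chemotherapy, which Section 2 puts at 12 to 20 or more weeks, so deletion could bring in mild chemotherapy events unrelated to the seed. Merely repeating the present exemption in Section 10 would remove the ambiguity but still allow mild related events to be left out.

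The cost is a wording change in two sections, slightly more data entry for 20 patients, and a partial reversal of a stated choice. Taken literally, the new limit also ends the exemption for unanticipated, unrelated AEs above mild. If the sponsor wants to keep that part, the same sentence should say so; the point made here does not depend on it.

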## 10. DATA MANAGEMENT & STATISTICAL CONSIDERATIONS

**Data Management:** The principle investigator and co-investigators will supervise the data collection management.

**Outcome analysis:** The successful placement of the Magseed into the metastatic axillary lymph node will be evaluated and recorded by the radiologist performing the procedure. This information will be document into the electronic medical records as per normal clinical practice, in addition this information stored in the database.

The degree in which the artifact created by the Magseed in the axilla obscures the axillary or adjacent breast findings will be evaluated and recorded by the radiologist interpreting the MRI. Treatment response based on mammographic and sonographic evaluation of the axilla will be evaluated and recorded by the radiologist. The radiologist will determine if the supplemental imaging with mammography and sonography adequately replaces visualization of the axilla on MRI. Imaging results will be records in standard radiological reports as well as the database.

The successful retrieval of the Magseed into the metastatic axillary lymph node will be evaluated by the surgeon and radiologist. These results will be reported in both the patients operative report as well as the research database.

**Adverse events:** Adverse events occurring during the research study will be recorded into the electronic medical records and recorded into the research database.

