An alternative to the radioactive seed is the Magseed (*Endomagetrics, Inc.*), a magnetic seed that uses an identical needle delivery system, that is FDA approved for long term placement into soft tissues prior to surgery. A recent study reported a 100% success rate of percutaneous preoperative localization of non-palpable breast lesions and surgical retrieval of the Magseed and intended breast target (7). However, given 3-4 cm of susceptibility artifact created by the Magseed on MRI, localization of the breast primary is recommended to be done only after all preoperative MR imaging is complete. The degree in which this artifact would interfere with the evaluation of the axilla is unknown as the axilla can also be evaluated with ultrasound to assess the response to NAC. MD Anderson currently is recruiting to an open label clinical trial evaluating placement of the Magseed into the axilla for preoperative localization after completion of NAC up to 30 days prior to surgery (NCT03038152). Recently, the Magseed was FDA cleared for soft tissues and long-term implementation, which means that the seed could be placed prior to initiation of NAC. Here at Mayo Clinic Rochester, the breast surgery group has a short-term trial approved to test the ease of use, intuitiveness, and accuracy of pre-surgical localization with the Magseed in the breast in our operating rooms, which would allow to also test the Magseed in the axilla.

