Placement of a Magseed prior to NAC in the biopsy proven metastatic lymph node at or close to the time of the lymph node sampling would allow the lymph node to be identified at surgery following NAC without requiring the patient to undergo a second preoperative localization procedure. This would eliminate the need for the potentially time consuming and frustrating search for the axillary biopsy clip in patients with an excellent treatment response. Feasibility of localizing the sampled lymph node would be substantially higher prior to NAC, but it is unknown if this benefit outweighs the potential loss of information in assessing the axillary response to NAC on MRI due to the susceptibility artifact created by the Magseed in the axilla. It is expected that there would be negligible artifact to the ipsilateral breast tissue so the response to NAC for the breast primary could still be assessed accurately on MRI, but this may depend on both the location of the primary breast tumor(s) and the metastatic axillary lymph node, and requires further evaluation.

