### 3. STUDY AIMS

**Aim 1:** Evaluate if Magseed is a viable alternative to radioactive seed as a localization method for biopsy proven metastatic breast carcinoma following neoadjuvant chemotherapy.

**Aim 2:** Determine the amount of artifact created by the Magseed in the axilla at MRI and identify imaging optimization to minimize the artifact produced by the magnetic clip.

**Aim 3:** Assess the success of retrieval of the Magseed and biopsy proven metastatic lymph node in the operating room compared to the current practice with the radioactive seed.

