## 5. STUDY DESIGN

**Part 1:** Ten women with biopsy proven breast cancer and metastasis to an axillary lymph node will have a Magseed placed into the metastatic lymph node AFTER neoadjuvant chemotherapy (NAC) and just prior to surgery. These patients will have a non-contrast enhanced breast MRI development study to evaluate and identify ways to reduce the artifact in the axilla created by the Magseed. Efficacy of the localization with the Magseed will be available within a week of the placement.

**Part 2:** Ten additional women with biopsy proven breast cancer and metastasis to an axillary lymph node will have a Magseed placed into the metastatic lymph node BEFORE NAC. These patients will have routine contrast enhanced MRIs, mammograms, and ultrasounds before and after NAC to evaluate treatment response.

**Seed placement:** Once a patient has been identified eligible for the research study and has provided written informed consent they will have a Magseed placed into the biopsy proven lymph node. The Magseed delivery system is identical to our current practice using radioactive seeds. The seed is pre-loaded into the needle and is inserted into the lymph node following local anesthesia with 1% lidocaine. Once the seed is deployed, post procedure seed location is confirmed sonographically and mammographically with tomosynthesis.

**MRI:** Ten no-charge limited non-contrast breast MRIs for research development purposes are available for this study through the radiology department. Phase 1 participants will enroll in the study after their pre- and post-NAC imaging has already been performed per routine clinical practice. These participants will have a single non-contrast enhanced breast MRI using our

standard non-contrast sequences (axial ideal T1 and T2-weighted, axial STIR, and axial 3D vibrant using a dedicated breast coil, FOV 28 cm or to fit the patient size, and an image-thickness/image-increment of 5mm/1mm). A physicist will participate in the scanning of these patients to evaluate the extent of artifact in the axilla and adjacent breast tissue and optimize scanning parameters to reduce this artifact.

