## 7. IMAGE INTERPRETATION

Experienced breast radiologists from our institution will place the Magseed into the axilla and interpret the MRI, mammographic and sonographic imaging as per current clinic practice. This

work flow will remain the same. The non-contrast enhanced breast MRI will be evaluated by both the study investigators and physicists.

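### Does Aim 2 need a defined artifact measurement and a compulsory same-patient comparison of MRI settings?

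*Combined protocol and SAP*

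**What the plan says.** Section 3, Aim 2: "Determine the amount of artifact created by the Magseed in the axilla at MRI and identify imaging optimization to minimize the artifact".

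Section 5 (MRI), on Part 1: "These participants will have a single non-contrast enhanced breast MRI". The scan uses the department's usual sequences, which the section lists, and a physicist takes part in order to "evaluate the extent of artifact in the axilla and adjacent breast tissue and optimize scanning parameters to reduce this artifact". Ten such scans are available, one per Part 1 patient.

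Section 7: "The non-contrast enhanced breast MRI will be evaluated by both the study investigators and physicists".

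Section 10 (Outcome analysis): "The degree in which the artifact created by the Magseed in the axilla obscures the axillary or adjacent breast findings will be evaluated". This task, and its entry in the record, falls to the radiologist who reads the MRI. The same paragraph has the radiologist judge whether mammography and ultrasound adequately stand in for MRI of the axilla.

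Section 2 holds the only artifact size in the documents, in a sentence about localizing the breast primary: "given 3-4 cm of susceptibility artifact created by the Magseed on MRI". It also names the trade-off in placing the seed before chemotherapy, the "potential loss of information in assessing the axillary response to NAC on MRI due to the susceptibility artifact". On artifact reaching the breast, it says "this may depend on both the location of the primary breast tumor(s) and the metastatic axillary lymph node, and requires further evaluation".

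The documents contain no sample-size justification, effect size, standard deviation or analysis method for artifact.

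**The concern.** Aim 2 promises an amount and a way of reducing it. An amount needs a unit, and a reduction needs a comparator. Section 10 offers an obscuration judgement without a scale. Section 5 speaks of extent and Section 7 of evaluation, neither with a unit, and Section 10 does not carry the physicist's assessment into the recorded outcomes. With one MRI per patient, it is easy to conclude that usual and tuned settings could be compared only across patients, where differences in anatomy might pass for an effect of the settings.

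If that were so, Part 1 could end with no artifact size to set beside 3-4 cm and no sound evidence that any setting helped. Section 6 relies on Part 1 to reduce artifact for the Part 2 patients, and Section 2 treats lost information on axillary response as the unknown to be weighed against early placement.

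**Working it through.** There is no stated calculation to reproduce: the ten Part 1 patients are given without a precision or power target. The check is therefore a reading of the artifact text, followed by arithmetic on assumed inputs.

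**1. Is a unit or scale missing?** Yes. Aim 2 says amount, Section 5 extent, Section 10 degree; none is defined.

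**2. Does one MRI per patient force a between-patient comparison?** No. An examination contains several acquisitions; Section 5 lists four sequence types (T1, T2-weighted, STIR, 3D vibrant). The usual sequences are the part that the text actually specifies for every Part 1 patient. Tuning by the physicist comes on top of them, in the same session. A usual acquisition beside a tuned one is the natural reading, although it is not written as a requirement.

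**3. Does Section 2 say artifact size varies with node position?** No. Its remark on location concerns whether artifact reaches breast tissue and affects assessment of the breast primary. It does not say that the diameter of the artifact changes with location.

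**4. How ambiguous would a comparison of two patients be?** Assume that 3-4 cm is spread between patients, so spread = 4 − 3 = 1 cm.
- No true effect: the observed difference lies between 3 − 4 = −1 and 4 − 3 = +1 cm.
- True 1 cm reduction: the tuned patient lies at 2-3 cm, so the difference lies between 3 − 3 = 0 and 4 − 2 = 2 cm.
- Overlap: 0 to 1 cm.

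With an assumed spread of 0.5 cm, the ranges are −0.5 to +0.5 and 0.5 to 1.5 cm, which meet only at 0.5 cm. The result depends on what the 3-4 cm range means, which the documents do not say, and it uses two patients where Part 1 has ten.

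**5. What would measurement and pairing offer?** Assumptions: two-sided 5% level, 80% power, and SD and within-patient correlation as shown.
- Mean size, n = 10: 95% half-width = t(0.975, 9)/√10 × SD = 2.262/3.162 × SD = 0.715 × SD. For SD 0.25, 0.5 and 1.0 cm this is 0.18, 0.36 and 0.72 cm.
- Paired, n = 10: detectable difference = 0.996 × SD of the differences, where that SD = SD × √(2(1 − ρ)). At SD 0.5 cm and ρ = 0.5 it is 0.5 × √1 = 0.50 cm, giving 0.996 × 0.50 = 0.50 cm.
- Unpaired, 5 against 5: 2.02 × SD, or 1.01 cm at SD 0.5 cm.

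Under these assumptions pairing about halves the detectable difference. That matters only if the trial would otherwise split patients between settings, and nothing in the plan says that it would.

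**6. What would a compulsory pair cost?** One modified version of one to four sequence types in ten patients is 10 × 1 = 10 to 10 × 4 = 40 extra acquisitions. Tuning may need more than one version. The documents do not give minutes per acquisition or the length of the free, limited sessions, and Section 6 notes that claustrophobia may end a scan.

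**The case for a change.** The strongest argument for a change is that one part of the loss could not be repaired. Size can be measured later on retained images, but a usual-setting acquisition that was never made cannot be recovered. Part 1 patients are scanned once, there are only ten free scans, and the seed comes out at surgery soon afterwards. Small numbers make a within-patient comparison more valuable, and asking for one requires no power calculation. An unscaled judgement by one radiologist is also hard to summarize across patients.

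Much of this stands as a description of the text. No unit is given, the rating has no scale, and keeping both acquisitions is not expressly required. A record of size and settings for each acquisition would be sound practice.

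The step to a defect in the plan does not stand. To lose the usual acquisition, the team would have to drop sequences that Section 5 lists for every Part 1 patient. The obscuration rating also bears directly on the question Section 2 poses, lost information on axillary response, and Section 10 adds a judgement on whether other imaging makes up for it. No section plans a comparison with 3-4 cm. Section 6 already states that Part 1 tuning is meant to benefit Part 2 scans, so the mention of usual clinical sequences for Part 2 in Section 5 is at most a missing cross-reference.

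**Conclusion.** No change to the plan is called for. Aim 2 is thinly specified, but followed as written the plan lets the physicist and investigators compare settings within a session and measure the artifact afterwards. Amending it would mainly write down a unit, a rating scale and a comparison that the design already implies, and the yield would be a descriptive listing in ten patients.

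The size of any harm cannot be established from the documents. The ambiguity of 0 to 1 cm exists only if the 3-4 cm range is spread between patients and settings are compared across two patients; at 0.5 cm spread it is confined to one value. The twofold gain from pairing rests on an assumed correlation of 0.5 and on an unpaired alternative that the plan does not propose.

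The conclusion rests on two assumptions: that the listed sequences are acquired and retained for each Part 1 patient, and that the physicist notes which settings were changed. Both are ordinary practice in a development scan. Safety and Aims 1 and 3 are not materially affected.
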